#### 4. Study Design Diagrams

[figure not shown]
[figure not shown]

Figure- Alternate analysis approaches

[figure not shown]
- ■ ■ ■ Included person-time
- ■ ■ ■ Excluded person-time

Provides 'on treatment' estimates for the outcome risk and addresses exposure person-time misclassification

### Analysis 1

[figure not shown]

### Analysis 3

[figure not shown]
Addresses misclassification of outcome onset

### Analysis 2

Addresses reverse causation due to preferential treatment initiation related to unrecorded cognitive impairment at study start and informative-censoring

### Analysis 4

Addresses outcome misclassification

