#### *Inclusion criteria for analyses 1, 3, 4:*

- Aged  $\geq 65$  years on the index date
- 365 days enrollment in Medicare Parts A, B, and D with no HMO coverage prior to index date
- No use of Anastrozole vs Exemestane or Letrozole, any time prior to index date (all available lookback approach with a minimum of 365 days)
- No diagnosis of dementia any time prior to and including index date
- No history of nursing home admission recorded in any time prior to and including index date
- At least two claims with breast cancer diagnosis recorded in 365 days prior to index date (ICD-9 174.x, 175.x, 233.0, V10.3 or ICD-10 C50.x19, C05.90, Z85.3)

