#### *Inclusion criteria for analysis 2:*

- Aged  $\geq 65$  years on the index date
- 365 days enrollment in Medicare Parts A, B, and D with no HMO coverage prior to index date
- No use of Anastrozole vs Exemestane or Letrozole, any time prior to index date (all available lookback approach with a minimum of 365 days)
- No diagnosis of dementia any time prior to and including index date
- No history of nursing home admission recorded in any time prior to and including index date
- At least two claims with breast cancer diagnosis recorded in 365 days prior to index date (ICD-9 174.x, 175.x, 233.0, V10.3 or ICD-10 C50.x19, C05.90, Z85.3)

- 180-day continuous use of Anastrozole vs Exemestane or Letrozole starting on the index date

c. Flowchart of the study cohort assembly

	Less Excluded Patients	Remaining Patients
All patients		23,466,175
Did not meet cohort entry criteria	-23,372,404	93,771
Excluded due to insufficient enrollment	-59,468	34,303
Excluded based on Dementia Exclusion	-4,796	29,507
Excluded based on Nursing Home Admission	-5,115	24,392
Excluded based on Breast Cancer Diagnosis	-5,939	18,453
Excluded anyone aged <65 at index	-1,464	16,989
Patients in Anastrozole group		10,926
Patients in Exemestane or Letrozole group		6,063
Final cohort		16,989

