Targeted therapy Antibody drug conjugates (Ado-trastuzumab emtansine, Fam-trastuzumab deruxtecan, Sacituzumab govitecan, Sacituzumab govitecan) Monoclonal antibodies (Trastuzumab, Pertuzumab, hyaluronidase, Margetuximab) Kinase inhibitors (Lapatinib, Neratinib, Tucatinib) CDK4/6 inhibitors (Palbociclib, ribociclib, abemaciclib) mTOR inhibitor (Everolimus) PI3K inhibitor (Alpelisib) PARP inhibitors (Olaparib, talazoparib)	Immunotherapy PD-1 inhibitor (Pembrolizumab)
Radiation therapy, beam therapy or brachytherapy	Breast surgery Lumpectomy Mastectomy

ICD-9, ICD-10, HCPCS, and NDC codes used to define the covariates listed above are available in Appendix A.

c. Outcome variables and study follow-up:

- **Primary outcome:** incident dementia, i.e., Alzheimer's disease, vascular dementia, senile, presenile, or unspecified dementia, or dementia in other diseases classified elsewhere. Outcome will be defined by 1 inpatient claim or 2 outpatient claims in analysis 1, 2, 3. In analysis 4, the outcome will be defined by 1 inpatient or 1 outpatient claims and 1 prescription claim for a symptomatic treatment [donepezil, galantamine, rivastigmine, and memantine] within 6 months of each other with outcome date assigned to second event in the sequence.
- Secondary outcomes: Individual component:  
Alzheimer's disease

Condition	ICD-9 and ICD-10 codes
Alzheimer's disease	331.0*, F00*, G30*
Vascular dementia	290.4*, F01*
Senile, presenile, or unspecified dementia	290.0*, 290.1*, 290.3*, 797*, F03*
Dementia in other diseases classified elsewhere	331.1*, 331.2*, 331.7*, 294.1*, F02*

For analysis 1,3, and 4 the follow-up will start the day after initiation of Anastrozole and Exemestane or Letrozole and will continue until the earliest date of the following events:

- The first occurrence of the outcome of interest
- The date of end of continuous registration in the database,
- End of the study period,
- Measured death event occurs,
- The date of drug discontinuation, defined as the date of the last continuous treatment episode of the index drug (Anastrozole and Exemestane or Letrozole) plus a defined grace period (i.e., 90 days after the end of the last prescription's days' supply in main analyses).

For analysis 2, the follow-up will start 180 days after initiation of Anastrozole and Exemestane or Letrozole and will continue until the earliest date of the following events:

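### Dementia-free entry is judged on diagnoses alone, so prior users of anti-dementia drugs can enter all four analyses, and Analysis 4 as written can pair a pre-index fill with a later diagnosis

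*Combined protocol and SAP*

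**What the plan says.** **Entry.** Section 5b has two inclusion lists, one for Analyses 1, 3 and 4 and one for Analysis 2. Both give the same dementia criterion: "No diagnosis of dementia any time prior to and including index date". The only drug-history criterion concerns the study drugs: "No use of Anastrozole vs Exemestane or Letrozole, any time prior to index date". Pharmacy data before entry are guaranteed by "365 days enrollment in Medicare Parts A, B, and D with no HMO coverage prior to index date". The flowchart in section 5c has one row, "Excluded based on Dementia Exclusion", with no further definition and no separate row for anti-dementia drugs.

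**Covariates.** The four anti-dementia drugs appear neither in the covariate list (section 6b) nor in the balance table (section 8).

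**Outcome.** Section 6c states: "Outcome will be defined by 1 inpatient claim or 2 outpatient claims in analysis 1, 2, 3". For Analysis 4 it adds "1 prescription claim for a symptomatic treatment [donepezil, galantamine, rivastigmine, and memantine"], and the diagnosis and the fill must lie "within 6 months of each other with outcome date assigned to second event in the sequence". Follow-up in Analysis 4 starts the day after drug initiation.

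**Purpose.** Section 4 says of Analysis 4: "Addresses outcome misclassification". It assigns to Analysis 2 the problem of reverse causation from cognitive impairment that was present but unrecorded at study start.

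**The concern.** In Analysis 4 the plan accepts a fill of one of these four drugs as evidence of dementia after the index date. It takes no account of the same fill before the index date, although at least 365 days of Part D data are in hand for every patient. Two things follow.

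- **Entry gap, all four analyses.** A patient already treated with one of these drugs but without a dementia code is classed as dementia-free. Matching cannot balance prior use directly, and section 8 would not reveal an imbalance.
- **Timing gap, Analysis 4 only.** Diagnoses up to the index date are excluded, so the fill is the one component that can come before it. The text allows a pre-index fill to be completed by the first post-index diagnosis, dated at that diagnosis. For a patient who keeps refilling, a fill lies close to almost any later claim, so the drug requirement adds little confirmation.

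At stake is whether the outcome is incident. The problem is most direct in the analysis that is meant to tighten the outcome definition.

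**Working it through.** The plan states no figure on this point, so the check is mainly of the wording.

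**1. Flowchart (section 5c).** 34,303 − 4,796 = 29,507, as printed. The dementia row removes 4,796 / 34,303 = 14.0%. The only definition the document gives for that row is the diagnosis criterion in section 5b.

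**2. The Analysis 4 rule applied to example timelines.** Index is day 0 and 6 months is taken as 183 days. Each patient has only the fill shown and a first dementia diagnosis on the day shown. The changed rule excludes anyone with a fill on or before day 0 and requires both events after day 0.

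| Fill (day) | Diagnosis (day) | Gap (days) | Case under current text | Case after change |
|---|---|---|---|---|
| −150 | +20 | 170 | yes | no |
| −30 | +150 | 180 | yes | no |
| −10 | +170 | 180 | yes | no |
| −100 | +80 | 180 | yes | no |
| −200 | +10 | 210 | no | no |
| +30 | +100 | 70 | yes | yes |

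**3. A timing clause alone is not enough.** Give the last patient an additional fill before the index date. The day +30 fill is now a refill. Both components still fall within follow-up, so a clause confined to timing would count this patient. Only the entry exclusion removes the case.

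**4. Analyses 1 to 3.** Here the fill plays no part in the outcome. A prior user becomes a case only through 1 inpatient or 2 outpatient dementia claims. In Analysis 2 follow-up starts at 180 days, but a prior user first coded on day 181 or later can still become a case.

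**5. Number of patients, under assumption.** The documents do not report prior fills. Section 9 takes the hazard ratios from the matched sample, 2 × 5,508 = 11,016.

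- Prior use 0.1%: 0.001 × 11,016 = 11 patients.
- Prior use 2%: 0.02 × 11,016 = 220 patients.

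On the unmatched cohort of 16,989 the same range is 17 to 340.

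**6. Effect on the hazard ratio, under further assumptions.** Suppose prior use is equal across arms and the events it produces occur at the same rate in both. Let s be their share of reference-arm events. Then, approximately, observed HR = s + (1 − s) × true HR. For an illustrative true HR of 0.80:

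- s = 3%: 0.03 + 0.97 × 0.80 = 0.806.
- s = 14%: 0.14 + 0.86 × 0.80 = 0.828.

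The documents give no value for s. Suppose half of prior users are later coded, genuine events occur at 5 to 10 per 1,000 person-years, and time on treatment is 1.5 years. Genuine events would then number 11,016 × 1.5 × 0.005 = 83 to 11,016 × 1.5 × 0.010 = 165. Treating s as the share of all events, it would run from 5.5 / (5.5 + 165) = 3% to 110 / (110 + 83) = 57%. That range is too wide to support any statement about size.

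**The case against.** The strongest reply is that this is silence and not an instruction. Section 6c calls the outcome incident dementia and starts follow-up the day after initiation, so a programmer could well look for both components within follow-up. The code list behind the flowchart's dementia row is not shown and might include drugs. Both points are fair. What is established is that the written plan neither excludes prior users nor fixes the timing of the first component. It is not established that the assembled cohort contains such patients. Even the favourable reading of the timing leaves refills by prior users, as step 3 shows.

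The wording of the Analysis 4 outcome can also be read as requiring the fill for every case, or only alongside an outpatient claim. The gap exists for outpatient cases under either reading.

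A reader might infer three stronger things that the documents do not support:

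- **That these events cannot be due to the study drug.** Some prior use may be off-label, and such a patient can later develop genuinely new dementia. Not every such case is false.
- **That reverse causation is brought back.** This would need prior use to differ between arms, and no difference is shown. Related crude covariates in section 8 are close, with standardised differences of −0.02 for depression, −0.02 for atypical antipsychotics and −0.06 for the frailty score. Anti-dementia fills themselves are not tabulated, so a difference is not ruled out either.
- **That all four analyses are equally affected.** The pre-index fill can count towards the outcome only in Analysis 4. The lag in Analysis 2 was designed for unrecorded impairment and deals with part of the problem.

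**Conclusion.** The point stands as a gap in the written criteria. Following section 5b admits patients already treated with drugs that section 6c itself uses as evidence of dementia, and nothing else in the plan screens or adjusts for them. The timing fault is specific to Analysis 4. In Analyses 1 to 3 the consequence is limited to prior users who later meet the diagnosis-claim definition.

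The number affected and the direction of any bias cannot be determined from the documents. The 11 to 220 matched patients rest wholly on an assumed prevalence of 0.1% to 2%. Dilution towards 1 is the likely main effect only if prior use is similar in the two arms; if it is not, the direction is open. The change should be made because the gap is plain on the text and cheap to close, not because a large bias has been shown.

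**What to change.** 1. Add to the inclusion criteria of all four analyses: *No dispensing of donepezil, galantamine, rivastigmine or memantine on or before the index date, using all available lookback.* Report the number excluded as its own flowchart row; that count also settles how large the problem was.
2. In the Analysis 4 outcome, state that both the diagnosis claim and the prescription claim must fall after the start of follow-up. With item 1 in place this follows automatically, but it lets the outcome definition stand on its own.
3. If Analysis 2 extends the drug exclusion to day 180, extend its diagnosis exclusion to the same day. The diagnosis exclusion now ends at the index date, and different windows would remove a patient for a day-90 fill but keep one with a day-90 diagnosis.
4. If the existing dementia exclusion already includes these drugs, one sentence in section 5b saying so replaces item 1.

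The cost is one filter on Part D data already required for eligibility, a rerun of the matching, and probably a small loss of patients, some of them treated off-label.

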### b. Primary endpoint

Incident dementia (i.e., Alzheimer's disease, vascular dementia, senile, presenile, or unspecified dementia, or dementia in other diseases classified elsewhere).

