## 3. Data Source(s)

Medicare, 2008-2018

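### The dementia code list includes ICD-10 F03 but omits ICD-9 290.2x and 294.2x, so the primary endpoint is not equivalent across the coding change inside the study period

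*Combined protocol and SAP*

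**What the plan says.** Section 1b defines the endpoint as incident dementia, comprising "Alzheimer's disease, vascular dementia, senile, presenile, or unspecified dementia, or dementia in other diseases classified elsewhere". Unspecified dementia is thus named as part of it.

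Section 6c turns this into codes. The row for senile, presenile and unspecified dementia is "290.0*, 290.1*, 290.3*, 797*, F03", and the row for dementia in other diseases is "331.1*, 331.2*, 331.7*, 294.1*, F02". The vascular row has 290.4 and F01; the Alzheimer's row has 331.0, F00 and G30. The claim rule is: "Outcome will be defined by 1 inpatient claim or 2 outpatient claims in analysis 1, 2, 3".

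At baseline, section 5b requires "No diagnosis of dementia any time prior to and including index date", with the same wording for analysis 2. No codes and no claim count are attached to this criterion. Appendix A is cited only for covariate codes.

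The data source in section 3 is "Medicare, 2008-2018", and the balance table in section 8 shows index years 2014 to 2018. The breast cancer criterion lists codes from both systems, so the plan expects claims in both.

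**The concern.** A code list that spans two coding systems should capture the same condition in each. Here the ICD-10 side captures unspecified dementia through F03. The ICD-9 side lists 290.0, 290.1, 290.3, 290.4 and 294.1 but skips 290.2x (senile dementia with delusional or depressive features) and 294.2x (dementia, unspecified). No reason is given.

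Two consequences follow, of different certainty:

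- **Outcome, whatever list governs the exclusion.** A new case coded only 290.2x or 294.2x before the change is not an event, or becomes one only when an ICD-10 code appears. The same case arising later counts at once.
- **Baseline, only if the exclusion uses the section 6c list.** A prevalent case with only those codes passes as dementia-free. When the condition is recoded F03 during follow-up, it counts as incident. Such events have nothing to do with either drug. They inflate incidence and dilute the comparison.

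Dilution matters in a study where a hazard ratio near 1 would itself be read as a finding.

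**Working it through.** **Code check.** I matched each code by prefix against every stem in the section 6c table. 290.20, 290.21, 294.20 and 294.21 match nothing. F03.90, 290.0 and 294.10 do match. The gap therefore lies across the whole table, not in one row only.

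**The plan's own figure.** The flowchart in section 5c reproduces: 34,303 − 4,796 = 29,507 after the dementia exclusion (4,796/34,303 = 14.0%), and the later steps lead to 16,989 = 10,926 + 6,063. These totals do not show which codes the exclusion used.

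**Share of patients exposed.** Inputs are the matched index-year counts in section 8 (anastrozole, comparator): 2014: 1,160 and 1,222; 2015: 1,217 and 1,211; 2016: 1,135 and 1,102; 2017: 1,001 and 992; 2018: 995 and 981. Assumptions: change on 1 October 2015, even accrual within each year.

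- Indexed before the change: anastrozole 1,160 + 0.75 × 1,217 = 2,072.75 (37.6% of 5,508); comparator 1,222 + 0.75 × 1,211 = 2,130.25 (38.7%). Together 4,203 of 11,016 = 38.2%.
- 365-day baseline straddling the change: 0.25 × 2,428 + 0.75 × 2,237 = 2,284.75, or 20.7%.
- 365-day baseline wholly in ICD-10: 0.25 × 2,237 + 1,993 + 1,976 = 4,528.25, or 41.1%.

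The baseline mechanism concerns mainly the first group. Later entrants can be excluded by an F03 code recorded before their index date.

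**Illustration of size.** The documents give no event counts, person-time or code-level counts, so every input here except the arm size (5,508) and the 38.2% share is an assumption:

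- true rate 10 to 20 per 1,000 person-years;
- mean follow-up 1 to 2 years;
- 0.25% to 2% of pre-change entrants with dementia coded only by the missing codes, all later recoded and counted, equally in both arms.

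Per arm, true comparator events t = 5,508 × rate × years, and false events f = 5,508 × 0.382 × proportion. The observed ratio is approximately (0.80 × t + f)/(t + f) for a true value of 0.80.

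- Mildest case: t = 5,508 × 0.020 × 2 = 220.3 and f = 5,508 × 0.382 × 0.0025 = 5.3. False share 5.3/225.6 = 2%; ratio (176.3 + 5.3)/225.6 = 0.805.
- Heaviest case: t = 5,508 × 0.010 × 1 = 55.1 and f = 5,508 × 0.382 × 0.02 = 42.1. False share 42.1/97.2 = 43%; ratio (44.1 + 42.1)/97.2 = 0.887.

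**The case against.** The strongest objection is that section 5b never says the exclusion uses the outcome table. If the exclusion uses a broader list, these prevalent cases are already out and the main source of dilution disappears. This stands. A reader might infer that patients with known dementia certainly enter and become false events. The documents support that only conditionally. The late or missed ascertainment of new cases does not depend on the exclusion list, although, if equal in both arms, it costs mainly events and timing.

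Second, several conditions must hold before a prevalent case becomes a false event. The patient must have no other listed code in the whole lookback and no nursing home record. An ICD-10 code must then appear, with enough claims, while the patient is followed: on treatment plus 90 days in analyses 1, 3 and 4, or up to 1,095 days in analysis 2. This stands, and makes the illustration an upper reading for each assumed proportion.

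Third, a reader might infer bias that differs by arm. Section 8 argues against it: after matching, 21.1% and 22.2% are indexed in 2014, and 22.1% and 22.0% in 2015.

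Fourth, a reader might suppose that 25% to 50% of events among early entrants are such cases, which turns 0.80 into 0.85 to 0.90 by (1 − f) × 0.80 + f, with f now that share. Nothing in the documents fixes that share, and the result would describe only the early entrants.

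The alternative analyses do not remove the problem. The 180-day lag in analysis 2 ends before October 2015 for anyone indexed before about April 2015. Analysis 4 adds a prescription requirement, but no criterion excludes prior use of those drugs, so a treated prevalent case newly coded F03 could qualify. Section 9 plans nothing by coding era.

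**Conclusion.** The gap is real and is a stated rule, not a missing detail: followed as written, the list ascertains the same named endpoint differently before and after the change. About 38% of matched patients entered before it. The consequence for the exclusion is conditional on section 5b using the same list. In that case the expected effect is inflated incidence and attenuation toward 1, with no clear direction favouring either drug.

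The size cannot be computed from the documents. The range of 0.805 to 0.887 for a true 0.80 shows that the effect could be negligible or material; it is not an estimate. The conclusion also rests on the meaning of the two code stems and the October 2015 date, which are standard coding facts that the documents do not state.

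A reader might go further and call the whole list unsound, because it counts 797 and lacks 331.82, G31.0, G31.1 and G31.83. That does not follow. Neither 331.82 nor G31.83 is listed, so adding them widens the endpoint without repairing an asymmetry. The absence of G31.0 and G31.1 is partly covered by F02. Keeping or dropping 797 is a choice about specificity, and dropping it would also loosen the exclusion if the lists are shared. The Alzheimer's row, used for the secondary outcome, shows no comparable gap.

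**What to change.** 1. Add 290.2x and 294.2x to the section 6c row.
2. State in section 5b the code list and claim rule for the dementia exclusion, and apply the same list there as for the outcome.
3. Rerun the exclusion, the propensity score match and balance table, and all four analyses.
4. Add a sensitivity analysis restricted to index dates whose 365-day baseline lies wholly in ICD-10. Matching is on the propensity score and not on index date, so rematch within this subset to avoid broken pairs.

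The cost is a code-list edit and a rerun. Some ICD-9-era patients move from the cohort to the exclusion, so the flowchart and matched sample sizes change. The sensitivity analysis keeps only about 41% of matched patients. Those indexed from October 2016 have at most about 2.25 years to the end of 2018, so it cannot inform the 3-year interval. Changes to 797, 331.82, G31.0, G31.1 and G31.83 are optional.

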## 6. Variables

### a. Exposure-related variables:

#### Study drug:

The study exposure of interest is initiation of Anastrozole

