#### Comparator:

Exemestane or Letrozole

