## 9. Statistical analysis plans

Incidence rates for the outcome will be estimated for the treatment and reference groups before and after PS matching. The competing risk of death could be of concern for the current set of analyses if mortality is frequent among patients included in the cohort and if differences in the risk of mortality between treatment and reference groups are substantial. In the PS-matched sample, we will use cause-specific hazard models to provide hazard ratios averaged over the entire follow-up period as well as interval specific hazard ratios (1, 2, and 3 years) for the association between the treatment of interest and risk of ADRD after considering all-cause mortality as a competing event. Pre-specified subgroup analyses will be conducted based on age, sex, and baseline cardiovascular disease.

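### In analyses 1, 3 and 4 the written censoring list does not end follow-up when a patient starts the other arm's drug, so some comparator-exposed time is credited to the index arm

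*Combined protocol and SAP*

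**What the plan says.** Section 6c sets one follow-up rule for three of the four analyses: "For analysis 1,3, and 4 the follow-up will start the day after initiation of Anastrozole and Exemestane or Letrozole". Follow-up ends at the earliest of five events: the outcome, loss of enrolment, the end of the study, death, or discontinuation of the index drug. Discontinuation is "defined as the date of the last continuous treatment episode of the index drug (Anastrozole and Exemestane or Letrozole) plus a defined grace period", and the grace period is "90 days after the end of the last prescription's days' supply in main analyses".

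The arms are defined in sections 6a and 5b. For the exposed arm, "The study exposure of interest is initiation of Anastrozole"; the comparator is "Exemestane or Letrozole", pooled. The only rule on use of the other arm's drug is the new-user criterion in section 5b, "No use of Anastrozole vs Exemestane or Letrozole, any time prior to index date", which looks backward from the index date.

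In section 4, the text beside Analysis 1 gives the purpose of the approach: "Provides 'on treatment' estimates for the outcome risk and addresses exposure person-time misclassification".

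**The concern.** A grace period is there to bridge refill gaps and to allow for a lingering effect of the drug just stopped. Under the written rule it also runs on after a recorded dispensing of the comparator. During that time the patient counts as exposed to one arm's drug while taking the other's. This is the exposure misclassification that the on-treatment approach is said to address. A patient who switches and then returns to her index drug within the grace period may never have the switch recognised at all.

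The bracket after the words on the index drug adds to the problem. It names the drugs of both arms, so a programmer could build an episode that continues across a switch. The 90-day limit would then no longer apply.

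The hazard ratios in section 9, both overall and by yearly interval, rest on this person-time. Analysis 2 does not censor at discontinuation, so it is no check free of switching.

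**Working it through.** The plan has no figure of its own to reproduce here, so the check is arithmetic on the stated rule.

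**Inputs from the documents (section 6c).** Grace period of 90 days from the end of the last days' supply; no censoring at a switch.

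**Step 1: misassigned days per switcher,** taking the episode to mean the patient's own index drug:

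days = max(0, unused supply at the switch + 90 − gap between end of supply and the switch)

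| Unused supply | Gap | Days credited to the wrong arm |
|---|---|---|
| 0 | 60 | 0 + 90 − 60 = 30 |
| 0 | 30 | 0 + 90 − 30 = 60 |
| 0 | 0 | 90 |
| 30 | 0 | 30 + 90 = 120 |
| 60 | 0 | 60 + 90 = 150 |
| 90 | 0 | 90 + 90 = 180 |

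An outcome, death, disenrolment or the study end can shorten any of these.

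**Step 2: share of an arm's person-time.** The documents give neither a switching rate s nor a mean on-treatment time T, so both are assumed. With d misassigned days per switcher, m = s × d / T.

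- Low: s = 0.10, d = 90, T = 730 days. m = 9/730 = 1.2%.
- High: s = 0.30, d = 90, T = 365 days. m = 27/365 = 7.4%.

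**Step 3: effect on the hazard ratio.** If m is equal in both arms and risk follows the drug currently taken,

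observed HR ≈ [HR(1 − m) + m] / [(1 − m) + m × HR].

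For a true HR of 0.80:

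- m = 1.2%: (0.7901 + 0.0123) / (0.9877 + 0.0099) = 0.804.
- m = 7.4%: (0.7408 + 0.0740) / (0.9260 + 0.0592) = 0.827.

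**Step 4: wider assumptions.** With s from 5% to 30%, d from 60 to 180 days and T from 1 to 3 years, m runs from 0.05 × 60/1095 = 0.3% to 0.30 × 180/365 = 14.8%. The observed HR then runs from 0.801 to 0.855.

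**Step 5: the cross-arm reading of the bracket.** Suppose switchers spend half of their follow-up on the other drug, again an assumption. Then m = s × 0.5, which is 5% to 15% for s of 10% to 30%. A true HR of 0.80 would appear as 0.818 to 0.856.

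**The case against.** The strongest reply concerns size and certainty. Several parts of it stand.

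- **The figures.** The design diagrams in section 4, with their key to included and excluded person-time, are not reproduced in the text available. A switching rule could be drawn there. The claim is therefore limited to the written list, which reads as complete.
- **The 90 days.** A reader might infer that every switcher has at least her last 90 days misassigned. The rule does not say that: the clock starts when supply ends, not at the switch, so a prior gap or an earlier censoring event shortens the time. Nor is 90 a ceiling, since unused supply adds to it.
- **Direction.** A reader might infer that the hazard ratio is always pulled toward 1, so that a null result could be put down to switching. That needs similar switching in both arms, switching unrelated to prognosis, and risk that follows the new drug at once. Dementia soon after a switch may partly reflect earlier index-drug exposure, which a grace period can be meant to capture.
- **Stated purpose.** The on-treatment aim stands beside Analysis 1. Analyses 3 and 4 share the censoring rule but have other stated aims, so the conflict with purpose is direct only for Analysis 1.
- **Informative censoring.** Ending follow-up at a switch may itself be informative, a concern that section 4 raises under Analysis 2.

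A reader might also want the words about the last treatment episode changed to the first. That concerns off-drug gaps and restarts, a separate question on which the switching argument has no bearing.

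None of this supplies the missing event. Nothing in the readable text says what happens when an other-arm drug is dispensed after the index date.

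**Conclusion.** The point holds for the written rule: in analyses 1, 3 and 4, time on the other arm's drug is credited to the index arm until 90 days after the index drug's supply ends. The omission changes which person-time is analysed, so it is more than missing detail. The likely bias is modest. In the 1.2-7.4% range, a true HR of 0.80 moves by 0.004 to 0.027, and that rests on assumed switching and follow-up as well as on the conditions for dilution given above. The documents do not show that the bias is large enough to turn a real difference into an apparent null. This should be fixed because the core exposure rule is incomplete, conflicts with the aim stated for Analysis 1, and can be programmed in more than one way.

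**What to change.** For analyses 1, 3 and 4:

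1. Add to the censoring list in section 6c, for both arms: *the date of first dispensing of a drug from the other arm*. Misassigned post-switch days then fall to zero.
2. State that moves between letrozole and exemestane count as staying in the comparator arm.
3. Reword the bracket so that the treatment episode refers only to the drug or drugs of the patient's own index arm.
4. Report the number of switchers by arm and, as a sensitivity analysis, either keep the current grace-period rule or apply inverse-probability-of-censoring weights.

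The cost is a few sentences and a rerun on claims data already held. The downsides are a small loss of person-time and possible informative censoring at the switch; item 4 is there to assess the latter. Whether to censor at once or after a lag is a design choice, and keeping the current rule as a sensitivity analysis shows how much it matters.
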